#### **Follow-up of unresolved adverse events**

Any AE/SAEs that are unresolved at the patient's end of treatment visit or safety follow up period during the study period are followed up by the investigator for as long as medically indicated, but without further recording in the eCRF. AstraZeneca retains the right to request additional information for any patient with ongoing AE(s)/SAE(s) at the end of the study, if judged necessary.

#### **Variables**

The following variables will be collected for each AE:

- AE (verbatim)
- the date and time when the AE started and stopped
- maximum intensity
- whether the AE is serious or not
- whether the AE is a suspected endpoint or not
- investigator causality rating against the Investigational Product (yes or no)
- action taken with regard to investigational product
- outcome.

In addition, the following variables will be collected for SAEs:

- Date AE met criteria for serious AE
- Date Investigator became aware of serious AE
- AE is serious due to (see definition in 6.4.2)
- Date of hospitalisation
- Date of discharge
- Probable cause of death
- Date of death
- Autopsy performed
- Causality assessment in relation to Study procedure(s)
- Causality assessment in relation to Other medication
- Description of AE.

The following definitions for intensity rating are:

1. mild (awareness of sign or symptom, but easily tolerated)
2. moderate (discomfort sufficient to cause interference with normal activities)
3. severe (incapacitating, with inability to perform normal activities)

It is important to distinguish between serious and severe AEs. Severity is a measure of intensity whereas seriousness is defined by the criteria in Section 6.4.2. An AE of severe intensity need not necessarily be considered serious. For example, nausea that persists for several hours may be considered severe nausea, but not a SAE. On the other hand, a stroke that results in only a limited degree of disability may be considered a mild stroke but would be a SAE.

### **Causality collection**

The Investigator will assess causal relationship between Investigational Product and each Adverse Event, and answer 'yes' or 'no' to the question 'Do you consider that there is a reasonable possibility that the event may have been caused by the investigational product?'

For SAEs causal relationship will also be assessed for other medication and study procedures. Note that for SAEs that could be associated with any study procedure the causal relationship is implied as 'yes'.

A guide to the interpretation of the causality question is found in Appendix B to the Clinical Study Protocol.

### **Adverse Events based on signs and symptoms**

All AEs spontaneously reported by the patient or reported in response to the open question from the study personnel: “Have you had any health problems since the previous visit/you were last asked?”, or revealed by observation will be collected and recorded in the CRF. When collecting AEs, the recording of diagnoses is preferred (when possible) to recording a list of signs and symptoms. However, if a diagnosis is known and there are other signs or symptoms that are not generally part of the diagnosis, the diagnosis and each sign or symptom will be recorded separately.

### **Adverse Events based on examinations and tests**

The results from protocol mandated laboratory tests and vital signs will be summarised in the clinical study report. Deterioration as compared to baseline in protocol-mandated laboratory values, vital signs and other safety variables should therefore only be reported as AEs if they fulfil any of the SAE criteria or are the reason for discontinuation of treatment with the investigational product.

If deterioration in a laboratory value/vital sign is associated with clinical signs and symptoms, the sign or symptom will be reported as an AE and the associated laboratory result/vital sign will be considered as additional information. Wherever possible the reporting investigator uses the clinical, rather than the laboratory term (eg, anaemia versus low haemoglobin value). In the absence of clinical signs or symptoms, clinically relevant deteriorations in non-mandated parameters should be reported as AE(s).

Any new or aggravated clinically relevant abnormal medical finding at a physical examination as compared with the baseline assessment will be reported as an AE.

Since ticagrelor is an anti-platelet agent, surveillance for possible bleeding events will be undertaken as follows:

All bleeding events that fulfil the criteria of an AE as judged by the investigator should be reported using the standard procedures for assessing severity, causality and seriousness. Some bleeding events may not be considered as AEs if the situation is not different from that expected by the investigator (eg, usual blood loss during CABG).

Bleeding AEs will be further classified as described in section 6.4.6.3.

#### **6.4.4 Reporting of serious adverse events**

All SAEs have to be reported, whether or not considered causally related to the investigational product, or to the study procedure(s). All SAEs will be recorded in the eCRF during the study period plus 7 day follow up. SAEs occurring in patients in the OLE or for unresolved SAE will be reported on a specific paper form and sent by fax to the AZ Patient Safety Data Entry Site.

If any SAE occurs in the course of the study, then investigators or other site personnel inform appropriate AstraZeneca representatives within one day ie, immediately but **no later than the end of the next business day** of when he or she becomes aware of it.

The designated AstraZeneca representative works with the investigator to ensure that all the necessary information is provided to the AstraZeneca Patient Safety data entry site within one calendar day of initial receipt for fatal and life threatening events and within five calendar days of initial receipt for all other SAEs.

For fatal or life-threatening adverse events where important or relevant information is missing, active follow-up is undertaken immediately. Investigators or other site personnel inform AstraZeneca representatives of any follow-up information on a previously reported SAE within one calendar day ie, immediately but no later than the end of the next business day of when he or she becomes aware of it.

Once the Investigators or other site personnel indicate an AE is serious in the WBDC system, an automated email alert is sent to the designated AstraZeneca representative.

If the WBDC system is not available, then the Investigator or other study site personnel should fax a paper back-up SAE report to the AstraZeneca representative immediately, recognizing that the same reporting time frames still apply. The Investigator or other study site personnel is responsible for completing the eCRF as soon as the system becomes available again.

The reference document for definition of expectedness/listedness is the SmPC or the Investigators Brochure (IB) for ticagrelor (AZD6140) in countries where it is appropriate.

#### **6.4.5 Reporting of suspected cardiac ischaemic events as adverse events**

Suspected cardiac ischaemic events should not be reported as AEs/SAEs. They are part of the natural history of the condition under investigation and therefore may be expected. All other events, with the exception of expected procedural-related bleeding events, will be reported as AEs/SAEs as detailed in Sections 6.4.3 and 6.4.4.

Once an event has been identified, using their clinical judgment, investigators must determine if the event could be classified as MI or recurrent cardiac ischaemia which lead to a stent thrombosis and/or an urgent revascularization.

#### **6.4.6 Definition and follow up procedures for Suspected Safety Endpoints:**

##### **6.4.6.1 Bleeding events: definition (according to PLATO)**

In this study bleeding events will be classified as shown below:

For patients experiencing a bleeding event that fulfils criteria in more than one category, the bleed will be assigned to the most severe category. This classification is a modification of the CURE definitions (Yusuf S et al 2001).

### **Major bleed – fatal/life-threatening**

Any one of the following:

- Fatal
- Intracranial
- Intrapericardial bleed with cardiac tamponade
- Hypovolaemic shock or severe hypotension due to bleeding and requiring pressors or surgery
- Clinically overt or apparent bleeding associated with a decrease in Hb of more than 50 g/La (3.1 mmol/Lb; 0.775 mmol/Lc)d
- Transfusion of 4 or more units (whole blood or packed red blood cells (PRBCs)) for bleeding.

### **Major bleed – other**

Any one of the following:

- Significantly disabling (eg, intraocular with permanent vision loss)
- Clinically overt or apparent bleeding associated with a decrease in Hb of 30 g/La (1.9 mmol/Lb; 0.465 mmol/Lc)d to 50 g/La (3.1 mmol/Lb; 0.775 mmol/Lc)d
- Transfusion of 2-3 units (whole blood or PRBCs) for bleeding.

### **Minor bleed**

- Requires medical intervention to stop or treat bleeding (eg, epistaxis requiring visit to medical facility for packing).

### **Minimal bleed**

All others (eg, bruising, bleeding gums, oozing from injection sites, etc) not requiring intervention or treatment.

### **Definitions of Terms**

a Reference range 130 to 180 g/L (males); 120 to 160 g/L (females)

b Reference range Hb tetramer 8.1 to 11.2 mmol/L (males); 7.4 to 9.9 mmol/L (females)

c Reference range Hb monomer 2.02 to 2.80 mmol/L (males); 1.85 to 2.47 mmol/L (females)

d To account for transfusions, Hb measurements will be adjusted for any PRBCs or whole blood given between 2 blood measurements. A transfusion of one unit of blood will be assumed to result in an increase of 10 g/La; 0.62 mmol/Lb; 0.155 mmol/Lc in Hb. Therefore, to calculate the true change in Hb if there has been an intervening transfusion between 2 blood measurements, the following calculations should be performed:

$\Delta \text{Hb} = [\text{baseline Hb} - \text{post transfusion Hb}] + [\text{number of transfused units} \times \text{conversion factor in Hb}^{\text{e}}]$

e Conversion factor = 10 g/La; 0.62 mmol/Lb; 0.155 mmol/Lc

**Bleeding** (either unexpected or of unanticipated quantity). If the patient experiences bleeding, he/she will be treated in accordance with local practice and the following data will be recorded:

- Last stable haemoglobin before start of bleeding (or hematocrit if hemoglobin unavailable). Hemoglobin (or hematocrit if hemoglobin unavailable) should be measured locally serially until resolution of the bleeding.
- Date, time and number of packed red blood cell or whole blood transfusions.

#### **6.4.6.2 Procedures for study medication in case of bleeding**

In case of a major bleed, study medication must be stopped immediately, but may be reinstated when the risk of bleeding is deemed low in the judgment of the Investigator. Major bleeding events should be managed according to need with general support and blood. The study medication administration need not be stopped in case of a minor bleeding. All bleedings should be treated and followed up according to local clinical practice. It should be noted that platelet transfusion may not reverse bleeding in a patient receiving ticagrelor as the new platelets may be inhibited by ticagrelor as long as it remains circulating in the blood.

There is no antidote to ticagrelor and treatment of bleedings should therefore be symptomatic and handled according to the clinical routines at the investigational site. For further details, refer to section 13.2.

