## **4.2 Exclusion criteria**

Patients should not enter the study (or for exclusion criterion n° 2, not continue in study) if any of the following exclusion criteria are fulfilled:

1. Expected time to 1st PCI balloon inflation in the hospital, from the qualifying ECG is more than 120 minutes.
2. Patient's refusal to sign full version of the Informed Consent Form before first intake of active ticagrelor 90 mg BID
3. Concomitant oral or intravenous therapy with strong cytochrome P450 3A (CYP3A) inhibitors which cannot be stopped for the course of the study.
  - Strong inhibitors: ketoconazole, itraconazole, voriconazole, telithromycin, clarithromycin (but not erythromycin or azithromycin), nefazadone, ritonavir, saquinavir, nelfinavir, indinavir, atazanavir, over 1 litre daily of grapefruit juice.
4. Contraindication to ticagrelor (e.g. hypersensitivity to the active substance or to any of the excipients, active pathological bleeding, history of previous intracranial bleed, moderate to severe hepatic impairment).
5. Patient who has received a loading dose of clopidogrel, prasugrel or ticagrelor (commercial pack) for the index event or who are on chronic treatment of prasugrel, clopidogrel or ticagrelor (commercial pack)
6. Concomitant medication that may increase the risk of bleeding [e.g non steroidal anti-inflammatory drugs (NSAIDs), oral anticoagulant and / or fibrinolytics, planned or administered 24 hours before randomization]
7. Planned surgery during the study period
8. Any of the following conditions in the absence of a functioning implanted pacemaker: known SSS, second or third degree AVB, or documented syncope of suspected bradycardic origin.
9. Patient requiring dialysis
10. Known clinically important thrombocytopenia
11. Known clinically important anemia

12. Known pregnancy or lactation
13. Condition which may either put the patient at risk or influence the result of the study (e.g., cardiogenic shock or severe hemodynamic instability, active cancer, risk for non-compliance, risk for being lost to follow up)
14. Active involvement in the planning and/or conduct of the study (applies to both AstraZeneca staff and/or staff at the study site)
15. Previous randomisation in the present study
16. Participation in another clinical study with an investigational product or device study during the last 30 days or during the study.

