## **5.8 Discontinuation of investigational product**

Patients may be discontinued from investigational product in the following situations:

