### **5.8.1 Temporary discontinuation of a patient from investigational product**

Severe thrombocytopenia (platelet count <50,000/uL). Patients may restart study medication once the severe thrombocytopenia resolves.

Major surgery or other non-cardiovascular invasive procedures, see 5.6.9

Major bleeding, see 6.4.6.3

If possible, treatment with study medication should be resumed until the completion of the study (i.e. 30 days post randomisation).

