### **5.8.2 Permanent discontinuation from study medication**

- Patient's decision: the patient is at any time free to discontinue treatment, without prejudice to further treatment.
- Incorrectly randomised patient in whom the inclusion/exclusion criteria violation would put the patient at undue risk
- Safety reasons as judged by the investigator (eg, clinically significant ventricular pauses, syncope related to bradycardia, persistent increase in serum creatinine level of clinical relevance, persistent, unexplained anaemia or thrombocytopenia
- Severe non-compliance to study protocol

All patients should remain in the trial and keep all visits whether they continue study medications or not.

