**Revised text:**

All patients should remain in the trial **and a follow up will be performed according to section 5.8.3 below, unless full Informed Consent is not signed** ~~and keep all visits whether they continue the study medication or not.~~

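### The protocol permits, though it does not require, restarting ticagrelor after an on-study intracranial bleed, which its own exclusion 4 treats as a contraindication

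*Protocol*

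**What the plan says.** - **Drug rule after a bleed (6.4.6.2).** "In case of a major bleed, study medication must be stopped immediately, but may be reinstated when the risk of bleeding is deemed low". The risk is judged by the investigator, and no type of major bleed is excepted.
- **Temporary discontinuation (5.8.1).** The list includes "Major bleeding, see 6.4.6.3". The section closes: "If possible, treatment with study medication should be resumed until the completion of the study", which it sets at 30 days after randomisation.
- **Bleeding definitions (6.4.6.1).** Intracranial bleeding is one of the criteria under "Major bleed – fatal/life-threatening". Any one criterion is enough.
- **Exclusion criterion 4 (4.2).** "Contraindication to ticagrelor (e.g. hypersensitivity to the active substance or to any of the excipients, active pathological bleeding, history of previous intracranial bleed".
- **Discontinuation in general (5.8).** The section opens permissively: "Patients may be discontinued from investigational product in the following situations".
- **Permanent discontinuation (5.8.2).** No bleeding event is named. The nearest entry is "Safety reasons as judged by the investigator", followed by examples. The later administrative change to 5.8.2 alters only the follow-up sentence ("a follow up will be performed according to section 5.8.3 below, unless full Informed Consent is not signed") and adds no reason for stopping.
- **Patients who develop an exclusion condition (end of 4.2, then 5.3).** The investigator informs the sponsor physician at once and the two discuss whether treatment continues. The investigator may stop the drug alone, and therapy stops if they cannot agree.
- **Maintenance treatment (5.5.2).** After the blinded loading doses, every patient in both arms takes active ticagrelor 90 mg twice daily.

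**The concern.** Exclusion 4 presents a previous intracranial bleed as a contraindication to the drug, not merely as an unsuitable entry characteristic. A patient who bleeds intracranially during the study has that history from then on. Yet the section an investigator would consult after a bleed allows the drug to be given again on a judgment of low risk, and 5.8.1 groups the event with reasons for a temporary pause.

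What is at stake is the safety of the individual patient. Because maintenance is active drug in both arms, every restart is a true re-exposure to ticagrelor. Section 6.4.6.2 itself notes that there is no antidote and that transfused platelets may not reverse the bleeding. A second intracranial bleed could be fatal or disabling, so one re-exposure matters even if such cases are very rare.

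**Working it through.** No arithmetic applies: the point depends on no rate, alpha or sample size. The check is a reading of the relevant sections together.

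**1. Does the restart permission reach intracranial bleeding?** Section 6.4.6.2 speaks of a major bleed without qualification. Section 6.4.6.1 makes an intracranial bleed major on that criterion alone, with no haemoglobin or transfusion threshold. Section 5.8.1 likewise refers to major bleeding as a whole. So the permission does reach it.

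**2. Is the permission compatible with exclusion 4?** The criterion lists both active pathological bleeding and a history of intracranial bleeding. Active bleeding resolves, so stopping and later restarting is coherent with it. A history does not resolve. For most major bleeds the present rule therefore fits the contraindication; for intracranial bleeds it does not.

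**3. Does any other section make the stop permanent?**

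| Section | What it adds | Rules out restart? |
|---|---|---|
| 4.2, opening | Applies the bar on continuing expressly only to criterion 2 | No |
| 4.2, end, and 5.3 | Sponsor notice, discussion, stop on disagreement, investigator may stop alone | No: continuing is one of the outcomes under discussion |
| 5.8, opening | Discontinuation is permitted | No |
| 5.8.2 | Discretionary safety clause; bleeding not named | No |
| Administrative change to 5.8.2 | Follow-up wording only | No |
| 6.3.2.2 | Defines haemorrhagic stroke by intracranial haemorrhage; requires neurological examination and brain imaging | No: no study-drug rule |
| 13.2 (cited in 6.4.6.2) | Overdose management | No |

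**4. Do the sections agree on who decides?** Under 6.4.6.2 the investigator alone judges whether the risk is low. Under 5.3 continuing needs agreement with the sponsor physician. Neither 6.4.6.2 nor 5.8.1 refers to 5.3, whose heading concerns incorrectly randomised patients. A reader who follows the bleeding section may not reach it.

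**5. How does the protocol treat other exclusions that arise on study?** Pregnancy is exclusion 12, and 13.3.1 calls for immediate discontinuation. Strong CYP3A inhibitors are exclusion 3, and 5.6.8.1 calls for interruption, with resumption if possible once the inhibitor is no longer needed. Both on-study rules match their exclusion. The rule covering intracranial bleeding does not.

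**6. Cross-reference.** Section 5.8.1 sends the reader to 6.4.6.3, which deals with recording and adjudicating bleeds. The rule on study drug is in 6.4.6.2.

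**The case against.** The strongest case on the other side is that the protocol already makes restart unlikely.

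- **The restart is guarded.** The immediate stop is compulsory, reinstatement is optional and needs a low bleeding risk, and 5.8.1 says only to resume where possible. With 30 days of treatment, an investigator would have to call the risk low within weeks of an intracranial bleed, knowing exclusion 4. This stands: restart would probably be rare. It does not remove the permission.
- **Section 5.3 applies.** Read with the end of 4.2, it covers a patient who develops an exclusion condition, and disagreement leads to a stop. This also stands, as partial protection. Agreement to continue remains open, and the bleeding section does not point to 5.3.
- **Permanent stopping is available.** The examples in 5.8.2 are not exhaustive, an intracranial bleed would normally be reported promptly as a serious adverse event (6.4.4), and a safety board reviews interim data (12.4). All true, but the first is discretionary and the other two are not rules about the individual patient's drug.
- **Other texts may say more.** The product label, the Investigator's Brochure and Appendix B are not at hand. The finding is therefore limited to the protocol text that can be read.

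Two stronger readings are tempting and are not supported. A reader might infer that the protocol instructs sites to resume ticagrelor after an intracranial bleed; the wording in 6.4.6.2 is permissive and that in 5.8.1 conditional. A reader might also infer that no safeguard exists; 5.3 and 5.8.2 show otherwise.

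**Conclusion.** The inconsistency holds in limited form. For intracranial bleeding the protocol permits restart of a drug that exclusion 4 calls contraindicated in a patient with that history. The available safeguards narrow this possibility without closing it.

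Its size cannot be stated as a number. The protocol gives no rate of intracranial bleeding and no basis for estimating how often an investigator would restart, so the count of affected patients may be zero. The weight comes from the severity of a single re-exposure. The efficacy endpoints, power and type I error are not touched.

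The conclusion rests on two assumptions: that exclusion 4 describes the drug's contraindications and so remains relevant after entry, as its wording indicates; and that no document outside the protocol imposes a binding permanent stop. The wrong cross-reference in 5.8.1 is clerical and adds no weight to the safety point, but it can be corrected in the same edit.

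**What to change.** Make four text changes in one amendment:

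1. **6.4.6.2:** add that after any intracranial bleed, including haemorrhagic stroke, study ticagrelor is stopped permanently. Keep the present rule for all other major bleeds.
2. **5.8.2:** list intracranial bleeding, including haemorrhagic stroke, as a reason for mandatory permanent discontinuation. The word mandatory is needed because the opening line of 5.8 is only permissive.
3. **5.8.1:** change the entry to *Major bleeding other than intracranial, see 6.4.6.2*, which also corrects the cross-reference.
4. **5.3:** add that the discussion on continuing or discontinuing does not apply to an on-study intracranial bleed, for which 5.8.2 governs. Without this, 5.3 would still leave continuation open for the same patient and contradict the first two edits.

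Patients who stop remain in follow-up under 5.8.3, so endpoint collection is unchanged. The cost is one amendment and a letter to sites, with no additional patients, visits or procedures.
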